6.5. Study intervention compliance

Participants will receive study intervention directly from qualified site staff and [REDACTED] [REDACTED] The date and time of each dose administered in the clinic will be recorded in the source documents. The dose of study intervention and study participant identification will be confirmed at the time of dosing by a member of the study site staff other than the person administering the study intervention.

6.6. Dose modification

Modifications to the dose are not applicable in this study.

6.7. Continued access to study intervention after the end of the study

Continued access to the investigational CAI (VH4004280 or VH4011499) after the end of the study is not permitted since therapeutic benefit has not yet been established.

The investigator is responsible for ensuring consideration has been given to the poststudy care and treatment of the participant's medical condition. The Sponsor recognizes some HIV-1 infected adults may encounter barriers to timely access to cART. Where it has been determined by the investigator to be an acceptable option, participants who have completed the study (i.e., Day 39 EOS which includes 10 days of double-blind monotherapy and 4 weeks of investigator chosen SOC) and are exercising reimbursement assistance from the Sponsor for their SOC, will have the option (but are not required) to receive up to an additional 3 months of reimbursement assistance post study. The investigator will choose the standard of care cART according to local treatment guidelines, accessibility and locally run genotypic/phenotypic results (if available).

6.8. Treatment of overdose

For this study, any dose of the CAI study intervention that exceeds the specified dose for that treatment group will be considered an overdose. In the event of an overdose, the investigator should:

- Contact the VH medical monitor immediately.
- Closely monitor the participant for any AE/SAE and laboratory abnormalities until study intervention can no longer be detected systemically, as medically appropriate.
- If requested by the VH medical monitor, obtain a plasma sample for PK analysis as soon as possible after the overdose. Intensive and single PK sampling is pre-specified as per the SoA (Section 1.3) such that an additional PK sample in the event of overdose may not be needed.
- Document the quantity of the excess dose as well as the duration of the overdose.

Decisions regarding investigations and management will be made by the investigator in consultation with the VH medical monitor based on the clinical evaluation of the participant, although VH/GSK does not recommend specific treatment for an overdose.

Refer to the approved product label for the cART standard of care for advice on overdose.

6.9. Prior and concomitant therapy

The VH medical monitor should be contacted if there are any questions regarding concomitant or prior therapy. Any medication or vaccine (including over-the-counter or prescription medicines, vitamins, and/or herbal supplements) that the participant is receiving at the time of enrollment or receives during the study must be recorded along with reason for use, dates of administration including start and end dates, and dosage information including dose and frequency.

- Acetaminophen/paracetamol at doses of ≤ 2 grams/day or nonsteroidal anti-inflammatory drugs (NSAIDs) are permitted for use any time during the study and their use documented in the CRF.

CCI

- No clinically significant interactions are expected following the start of any anticipated cART standard of care regimen on Day 11.

CCI

7. DISCONTINUATION OF STUDY INTERVENTION AND PARTICIPANT DISCONTINUATION/WITHDRAWAL

7.1. Discontinuation of study intervention

Discontinuation of study intervention refers to any participant who has not received all planned doses of the study intervention CCI

Despite the study intervention being permanently discontinued, the participant should remain in the study, continue to comply with all other aspects of the protocol (such as starting the first dose of cART standard of care on Day 11) and be followed according to the SoA (Section 1.3) to the EOS as defined in the protocol. [REDACTED]

[REDACTED]

[REDACTED]

If participants prematurely discontinue study treatment prior to Day 11 (primary endpoint), participants may be replaced at the discretion of the Sponsor in consultation with the investigator. Participants will not be replaced if the reason for discontinuation from the study treatment is due to a safety concern which the investigator considers reasonably attributable to study treatment e.g., when a participant meets stopping criteria. Refer to Section 7.1.1 (Liver chemistry stopping criteria), Section 7.1.2 (QTc stopping criteria) and Section 7.2.1 (SARS-CoV-2 management criteria).

The primary reason for premature discontinuation of the study intervention will be documented in the eCRF based on the list below:

Reasons	Additional items/Sub-reasons
AE	
Death	
Participant Reached Protocol-Defined Stopping Criteria	Specify
Lack of efficacy	
Lost to follow-up	
Physician Decision	Specify
Protocol Deviation	Specify
Withdrawal by Participant	Specify
Other	Specify

7.1.1. Liver chemistry stopping criteria

Liver stopping and increased monitoring criteria have been designed to assure participant safety and evaluate liver event etiology, in alignment with the FDA premarketing clinical liver safety guidance:

<https://www.fda.gov/regulatory-information/search-fda-guidance-documents/drug-induced-liver-injury-premarketing-clinical-evaluation>

If a participant meets the liver chemistry stopping criteria (i.e., ALT \geq 3xULN) further CAI dosing should be discontinued if applicable [REDACTED]

[REDACTED] and the participant will be monitored as detailed in Section 10.6.

CCI

[REDACTED] In the presence of abnormal liver chemistries that do not meet the protocol-specified liver chemistry stopping rule, the investigator may choose to discontinue further study treatment if the investigator believes that it is in best interest of the participant.

Refer to Section [8.3.7](#) for information about study pausing criteria.

7.1.2. QTc stopping criteria

A participant that meets any of the bulleted criterion based on the average of triplicate ECG readings will have met a QTc stopping criterion.

- QTcF >500 msec,
- Change from baseline: QTcF >60 msec

If a QTc stopping criteria is met or another clinically significant finding is identified, then the investigator in consultation with the VH medical monitor will determine if any change in participant management is needed and if the participant can continue the study intervention. Any new clinically relevant finding should be reported as an AE.

Refer to Section [8.3.7](#) for information about study pausing criteria.

7.1.3. Pregnancy

Participants who become pregnant during the study should discontinue. Refer to Section [8.4.5](#) for further details.

7.1.4. Temporary discontinuation

Temporary discontinuation of either VH4004280/placebo or VH4011499/placebo is not allowed in this study.

7.1.5. Rechallenge

Rechallenge with either VH4004280/placebo or VH4011499/placebo is not allowed in this study.

7.2. Participant discontinuation/withdrawal from the study

- A participant may withdraw from the study at any time at their own request for any reason (or without providing any reason) or may be withdrawn at any time at the discretion of the investigator for safety, behavioral, or compliance reasons.
- Discontinuing from the study for safety reasons should be infrequent. As described in Section 7.1, participants who meet a safety stopping criteria or who discontinue study intervention due to a safety reason, should remain in the study, continue to comply with all other aspects of the protocol (such as starting the first dose of cART standard of care on Day 11) and be followed according to the SoA (Section 1.3) to the EOS as defined in the protocol.
- Participants will not be replaced if the reason for discontinuation from the study is due to a safety concern, with the exception of SARS-CoV-2 scenarios as described in Section 7.2.1. If participants prematurely discontinue the study for non-safety reasons prior to Day 11 (primary endpoint), additional replacement participants may be enrolled at the discretion of the sponsor and investigator. These replacement participants will be assigned to the same treatment sequence and same dose as the corresponding participant who prematurely discontinued from the study.
- Investigators will contact participants who do not return for scheduled visits or follow-up and encourage protocol compliance.
- At the time of discontinuing from the study, if possible, an early discontinuation visit should be conducted, as shown in the SoA (Section 1.3). The SoA lists the data to be collected at the time of study discontinuation and follow-up and for any further evaluations that need to be completed.
- All data and samples collected up to and including the date of withdrawal of/last contact with the participant will be included in the study analyses. If the participant withdraws consent for disclosure of future information, the sponsor may retain and continue to use any data collected before such a withdrawal of consent.
- If a participant withdraws from the study, the participant may request destruction of any samples taken and not tested, and the investigator must document this in the site study records.
- The primary reason for participant discontinuation/ withdrawal from the study will be documented in the eCRF. Participants who are withdrawn from the study because of AEs/SAEs must be clearly distinguished from participants who are withdrawn for other reasons. Investigator will follow participants who are withdrawn from the study due to an AE/SAE until the event is resolved (refer to Section 10.3.6).

7.2.1. SARS-COV-2 Management Criteria

A participant who is found to have SARS-CoV-2 infection during the study may proceed in the study at the discretion of the investigator and sponsor assuming the participant isolates according to current Centers for Disease Control and Prevention guidance and then has a repeat SARS-CoV-2 test that is negative. Otherwise, participants who are withdrawn from the study due to SARS-CoV-2 infection (including exposure to SARS-CoV-2) may be replaced based upon the discretion of the sponsor and investigator.

Refer to Section 10.9 for further details regarding the conduct of the study when impacted by SARS-CoV-2 infections and/or exposures.

7.3. Lost to follow-up

A participant will be considered lost to follow-up if the participant repeatedly fails to return for scheduled visits and is unable to be contacted by the study site.

The following actions must be taken if a participant fails to return to the clinic for a required study visit:

1. The site must attempt to contact the participant and reschedule the missed visit as soon as possible, counsel the participant on the importance of maintaining the assigned visit schedule and ascertain whether the participant wishes to and/or should continue in the study.
2. Before a participant is deemed lost to follow-up, the investigator or designee must make every effort to regain contact with the participant (where possible, 3 telephone calls, and if necessary, a certified letter to the participant's last known mailing address or local equivalent methods). These contact attempts should be documented in the participant's medical record.
3. Should the participant continue to be unreachable, the participant will be considered to have withdrawn from the study.
4. Site personnel, or an independent third party, will attempt to collect the vital status of the participant within legal and ethical boundaries for all participants randomized, including those who did not get study intervention. Public sources may be searched for vital status information. If vital status of the participant is determined as deceased, this will be documented and the participant will not be considered lost to follow-up. Sponsor personnel will not be involved in any attempts to collect vital status information.

8. STUDY ASSESSMENTS AND PROCEDURES

5. Study procedures and their timing are summarized in the [Schedule of activities \(SoA\)](#) (Section 1.3). Protocol waivers or exemptions are not allowed.
6. Adherence to the study design requirements, including those specified in the SoA (Section 1.3), is essential and required for study conduct.
7. All screening evaluations must be completed and reviewed to confirm that potential participants meet all eligibility criteria. Participants who have signed informed consent but are not eligible to proceed should be recorded in the eCRF with a status of 'screen failure'.
8. Procedures conducted as part of the participant's routine clinical management [(e.g., blood count)] and obtained before signing of the ICF may be utilized for screening or baseline purposes provided the procedures met the protocol-specified criteria and were performed within the timeframe defined in the SoA (Section 1.3).

9. In the event of a significant study-continuity issue (e.g., caused by a pandemic), alternate strategies for participant visits, assessments, study intervention distribution and monitoring may be implemented by the sponsor or the investigator, as per local health authority/ethics requirements. Refer to Section 10.10 for more information.
10. The maximum amount of blood collected from each participant over the duration of any 56-day period will not exceed 500 mL.
11. Repeat or unscheduled samples may be taken for safety reasons or for technical issues with the samples.
12. Pharmacokinetic results that could unblind the study will not be reported to investigative sites or other blinded personnel.

8.1. Administrative and baseline procedures

8.1.1. Collection of demographic data

Record demographic data such as year of birth, sex at birth, current sex, current gender identity, race, and ethnicity in the participant's eCRF. Collection of these demographic data is necessary to assess and monitor the diversity of the trial participants, and to determine if the trial participants are truly representative of the intended impacted population.

8.1.2. Medical/vaccination history

Obtain the participant's medical and disease history by interviewing the participant and/or review of the participant's medical records. Also obtain the participant's SARS-CoV-2 vaccination history. Record any pre-existing conditions (including reasons for taking concomitant medications), signs and/or symptoms present prior to the first dose of study intervention in the eCRF.

8.2. Efficacy assessments

Planned timepoints for all efficacy assessments are provided in the SoA (Section 1.3).

8.2.1. Quantitative HIV-1 RNA

Plasma for quantitative HIV-1 RNA will be collected at timepoints listed in Section 1.3. An HIV-1 RNA PCR assay (Cobas HIV-1) with a linear range of 20 to 10,000,000 copies/mL will be used. Details concerning the handling, labeling and shipping of these samples to the central laboratory will be supplied in the Laboratory Manual.

8.2.2. Lymphocyte Subsets by Flow Cytometry

Blood samples will be obtained from each participant for the analysis of lymphocyte subsets by flow cytometry at the timepoints listed in Section 1.3. Details concerning the handling, labeling and shipping of these samples will be supplied in the Laboratory

Manual. Refer to the List of Clinical Laboratories and Key Vendors document for laboratory names and addresses of the clinical laboratories used in this study.

8.3. Safety assessments

Planned timepoints for all safety assessments are provided in the SoA (Section 1.3).

8.3.1. Physical examination

- A complete physical examination will include, at a minimum, assessments of the skin, cardiovascular, respiratory, gastrointestinal, and neurological systems.
- A brief physical examination is symptom driven (with the exception of an expected respiratory system assessment at select visits) and may be targeted to include select system/organ assessments. At the discretion of the investigator, a brief physical examination may be made a complete physical examination.
- Investigators should pay special attention to clinical signs related to previous serious illnesses.
- Height and weight measurements will be used to calculate body mass index (BMI).

8.3.2. Vital signs

- Vital signs (to be taken before blood collection for laboratory tests) will consist of body temperature, single pulse rate, respiratory rate and blood pressure measurement.
- Body temperature will be assessed as per site's standard practice and should be measured at the same location throughout the study. Blood pressure and pulse measurements should be preceded by at least 5 minutes of rest for the participant in a quiet setting without distractions (e.g., television, cell phones). Blood pressure and pulse measurements will be assessed in a semi-supine position with a completely automated device. Manual techniques will be used only if an automated device is not available.
- If abnormalities in pulse or blood pressure are noted, repeat recordings should be measured in triplicate, at least 1 minute apart. The average of the 3 readings will be recorded in the eCRF.

8.3.3. Electrocardiograms

Single 12-lead ECG tracings will be obtained as outlined in the SoA (Section 1.3) using an ECG machine that automatically calculates the heart rate and measures PR, QRS, QT, and QTc intervals. Each ECG recording will be obtained after the participant has been in a semi-supine position for at least 5 minutes. The ECG should be read locally. Contact the VH medical monitor with any concerns.

Under certain circumstances the ECG should be repeated twice more (triplicate obtained) with recordings obtained as closely as possible in succession. Data from the average of 3

ECGs will be used for any action taken. Triplicate ECGs should be obtained if the investigator determines an ECG abnormality is clinically significant or if the investigator is unable to determine the significance of abnormalities relating to rate, rhythm, or intervals (including prolongation of the QT interval),

Refer to Section 7.1.2 for QTc stopping criteria for further details.

8.3.4. Clinical safety laboratory tests

- Refer to Section 10.2 for the list of clinical safety laboratory tests to be performed by the central laboratory in accordance with the Lab Manual and the SoA (Section 1.3). Refer to the List of Clinical Laboratories and Key Vendors document for laboratory names and addresses of the clinical laboratories used in this study.
- A point of care SARS-CoV-2 validated test will be run locally to determine eligibility on Day 1. Sites should adhere to the manufacturers guidance for which samples are allowed (e.g., nasopharyngeal, oropharyngeal).
- The investigator must review the laboratory results, document this review, and record any clinically significant changes occurring during the study as an AE. The laboratory results must be retained with source documents.
- All laboratory tests with values considered clinically significantly abnormal from dosing of the study intervention until the EoS visit (i.e., Day 39) should be repeated until the values return to normal or baseline or are no longer considered clinically significant by the investigator or VH medical monitor.
- In the absence of a diagnosis, abnormal laboratory findings assessments or other abnormal results the investigator considers clinically significant will be recorded as an AE or SAE, if they meet the definition of an AE or SAE (refer to Section 10.3.1 and Section 10.3.2).
- If clinically significant values do not return to normal/baseline within a period of time judged reasonable by the investigator, the etiology should be identified, and the sponsor notified.
- If laboratory values from non-protocol-specified laboratory tests performed at the institution's local laboratory require a change in participant management or are considered clinically significant by the investigator (e.g., SAE or AE), then the results must be recorded.

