
 Repeat liver chemistries (include ALT, aspartate transaminase [AST], alkaline phosphatase, total bilirubin and INR) and perform liver event follow up assessments within 24 hours. Monitor participant twice weekly until liver chemistries resolve, stabilise or return to within baseline. A specialist or hepatology consultation is recommended. 
If $ALT \geq 3 \times ULN$ AND total bilirubin $< 2 \times ULN$ and INR ≤ 1.5:
 
 Perform liver chemistries (include ALT, AST, alkaline phosphatase, total bilirubin and INR) and perform liver event follow up assessments within 24-72 hours. Monitor participant weekly until liver chemistries resolve, stabilize or return to within baseline. 	
gamma-glutamyl transferase (GGT), glutamate dehydrogenase (GLDH) and serum albumin.
 
 Fractionate bilirubin¹ if total bilirubin $\geq 1.5 \times ULN$. Obtain complete blood count with differential to assess eosinophilia. Record the appearance or worsening of clinical symptoms of liver injury, or hypersensitivity, fatigue, decreased appetite, nausea, vomiting, abdominal pain, jaundice, fever, or rash on the liver event eCRF form. Record use of concomitant medications on the concomitant medications report form including acetaminophen, herbal remedies, recreational drugs, and other over the counter medications Record alcohol use on the liver event alcohol intake eCRF form 
If $ALT \geq 3 \times ULN$ AND total bilirubin $\geq 2 \times ULN$ or INR > 1.5 obtain the following in addition to the assessments listed above:
 
 Anti-nuclear antibody, anti-smooth muscle antibody, Type 1 anti-liver kidney microsomal antibodies, and quantitative total immunoglobulin G (IgG) or gamma globulins Serum acetaminophen adduct assay should be done (where available) to assess potential acetaminophen contribution to liver injury unless acetaminophen use is very unlikely in the preceding week (e.g., where the participant has been resident in the clinical unit throughout). The site must contact the VH medical monitor when this test is required

Liver Chemistry Monitoring/Stopping Criteria	
	
 • Liver imaging (ultrasound, magnetic resonance, or computed tomography) and /or liver biopsy⁵ to evaluate liver disease; complete Liver Imaging and/or Liver Biopsy eCRF forms.

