4.3.2.2. Liver panel laboratory analyses

Change from baseline values for liver panel laboratory parameters will be summarised by visit. Visits up to Day 11 (inclusive) will exclude any liver panel values assessed under SoC, if SoC starts earlier for any reason, in line with the Estimand definition (Section 1.1.1).

Laboratory toxicities will be graded according to the DAIDS Criteria Version 2.1.

For liver panel lab tests that are gradable by DAIDS (e.g. ALT, AST), summary of worst-case grade increase from baseline grade will be provided. This summary will display the number and percentage of participants with a maximum post-baseline grade increase from their baseline grade (e.g. for participants with maximum increase from Baseline to grade 4 the number and percentage of them will be displayed, same for increase to grade 3, 2 and 1). Also, maximum increase subtotals (i.e. max increase in grade to any grade between 1 and 4, max increase to grade 2-4 or max increase to grade 3-4) will be included. The grade increases are determined by comparing the baseline grade to the worst-case post-baseline grade (e.g., Increase to Grade 1, Increase to Grade 2 etc.) and maximum grade increase subtotals (e.g., Increase to Grades 1 to 4, Increase to Grades 2 to 4, Increase to Grades 3 to 4). The grading subtotals are determined by adding the counts for each worst-case grade change within the subtotal category, e.g., 'Increase to Grades 1 to 4' is a subtotal of all worst-case increases to Grade 1, to Grade 2, to Grade 3, and to Grade 4. Participants with missing baseline value are to be assumed to have a Grade 0 at baseline. The determination of the worst case during the post-baseline period takes into account both planned and unscheduled assessments.

This summary will be produced while participants are under the monotherapy period, as well as overall (i.e. monotherapy and Follow-Up periods).

Liver panel data for participants with at least one abnormal lab value will be included in the listing of chemistry laboratory parameters.

More details of all planned displays are provided in the OPS document.

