6.2.4. Assessment Window

For data summaries by visit, all visit assessments (including those from planned, unscheduled and withdrawal visits) will be slotted into a target visit based on visit window defined in the table below. Within each study period, if there are multiple assessments within the same analysis visit window, the following hierarchy will determine which assessment will be used:

1. The assessment that is closest to the target day.
2. If there are multiple assessments equidistant from the target day, then:
 - a. for continuous parameters the average of the values will be used
 - b. for categorical parameters the worst assessment will be used.

The following analysis visit windows will be used for all but PK data

Analysis Set / Domain	Parameter (if applicable)	Target	Analysis Window		Analysis Timepoint
			Beginning Timepoint	Ending Timepoint	
All but PK	All	Study Day 1	≤ Study Day 1		Baseline
		Study Day 2	Study Day 2	Study Day 2	Day 2
		Study Day 4	Study Day 3	Study Day 5	Day 4
		Study Day 6	Study Day 6	Study Day 6	Day 6
		Study Day 7	Study Day 7	Study Day 7	Day 7
		Study Day 9	Study Day 8	Study Day 10	Day 9
		Study Day 11	Study Day 11	Study Day 11	Day 11
		Study Day 18	Study Day 15	Study Day 21	Day 18
		Study Day 25	Study Day 22	Study Day 28	Day 25
		Study Day 32	Study Day 29	Study Day 35	Day 32
		Study Day 39	Study Day 36	Study Day 42	Day 39

Assessments performed on Study Days 12, 13, 14 or after Study Day 42 will not be included in 'by visit' data summaries.

CCI

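### SAP 6.2.4 lets abnormality-triggered repeats compete with scheduled samples, so the value entering the by-visit liver-panel summary can depend on the outcome

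*Protocol*

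**What the plan says.** **Where repeats come from.** Protocol 8.3.4 covers values judged clinically significantly abnormal between dosing and Day 39; these "should be repeated until the values return to normal or baseline or are no longer considered clinically significant by the investigator", or by the medical monitor. Protocol 10.6 requires a liver recheck once ALT reaches 3×ULN. If bilirubin and INR stay below their limits, the site is to "Perform liver chemistries (include ALT, AST, alkaline phosphatase, total bilirubin and INR) and perform liver event follow up assessments within 24-72 hours", and otherwise the recheck is due within 24 hours. Protocol Section 8 also allows others: "Repeat or unscheduled samples may be taken for safety reasons or for technical issues with the samples".

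**How they enter the analysis.** SAP 6.2.4 states that "all visit assessments (including those from planned, unscheduled and withdrawal visits) will be slotted into a target visit based on visit window". When a window holds several values, the first choice is "The assessment that is closest to the target day". If they are equidistant, "for continuous parameters the average of the values will be used".

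**What uses the result.** SAP 4.3.2.2: "Change from baseline values for liver panel laboratory parameters will be summarised by visit". This is one of the two liver-panel secondary endpoints. The other, worst-case grade increase, takes planned and unscheduled values together.

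**The concern.** Most liver repeats exist because an earlier value was abnormal. A rule that lets a repeat stand in for a scheduled value therefore makes the choice of value depend on the outcome. When a scheduled sample is taken early in its window and is abnormal, the recheck it triggers is often nearer the target day and takes its place. A normal sample on the same day triggers no recheck and stays.

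Rechecks tend to be lower than the value that prompted them, through regression to the mean and because retesting continues until the value settles. Liver injury is a named risk in Protocol 2.3.1 and each dose arm has 6 participants, so one substituted value can visibly move an arm's mean and maximum at a visit.

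**Working it through.** The plan gives no figure for this. The check enumerates SAP 6.2.4's own windows.

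**1. Windows that can be affected.** Days 2, 6, 7 and 11 are single-day windows, so a later-day repeat cannot displace those values. Days 4 and 9 span target ±1 day; Days 18, 25, 32 and 39 span target ±3 days. Six of the ten post-baseline windows are therefore exposed. After Day 11, Days 12 to 14 lie outside every window.

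**2. Rule.** Let s be the scheduled day and r the repeat day, both measured from the target, with r = s + lag. The scheduled value is displaced if |r| < |s|, averaged if |r| = |s|, and kept if |r| > |s|. Because r > s, displacement needs s < 0, that is, an early visit.

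**3. Assumptions.** The documents give no distribution of visit days or lags. I take s as uniform over the permitted days and the lag as 1, 2 or 3 days with equal chance.

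**4. Effect on the triggering value.**

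| Window | Pairs | Displaced | Averaged | Kept | Repeat outside window |
|---|---|---|---|---|---|
| Follow-up, ±3 | 7 × 3 = 21 | 7 (33%) | 1 (5%) | 7 | 6 |
| Days 4 and 9, ±1 | 3 × 3 = 9 | 1 (11%) | 1 (11%) | 1 | 6 |

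By lag of 1, 2 and 3 days, the follow-up displacement is 3/7, 2/7 and 2/7 (43%, 29%, 29%). Among early follow-up visits only, it is 7/9 (78%). At Days 4 and 9 the only displacing case is a repeat exactly one day later (Day 3 then 4, or Day 8 then 9).

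**5. Spill into the next window.** A Day 2 abnormality repeated on Days 3, 4 or 5 meets a scheduled Day 4 visit held on Days 3, 4 or 5. Counting only scheduled samples taken after the repeat, 1 of 9 pairs is displaced (repeat Day 4, visit Day 5) and 1 of 9 averaged (Days 3 and 5). Day 7 into the Day 9 window is identical.

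In follow-up, the six out-of-window pairs land in the next window at −3 (three pairs), −2 (two) and −1 (one), except after Day 39, which has no next window. With the next visit uniform over seven days, a later scheduled value is displaced in (2×1 + 1×2)/(21×7) = 4/147 (3%) and averaged in (3 + 2 + 1)/147 = 6/147 (4%). Spill is thus minor in follow-up, but as large as the direct effect for the Day 4 and Day 9 windows.

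**6. Size of one substitution.** Assume an arm of 6 with one ALT of 140 U/L from a baseline of 25 U/L, the others unchanged. The arm mean change is (140 − 25)/6 = 19.2 U/L. A simulation with no drug effect (lognormal ALT, median 25, ULN 40, between-person log SD 0.6 to 0.8, within-person 0.25 to 0.35, first value at least 120) puts the repeat at about 69% to 89% of the first value. The mean change then becomes:

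- at 69%: (96.6 − 25)/6 = 11.9 U/L, a fall of 38%;
- at 89%: (124.6 − 25)/6 = 16.6 U/L, a fall of 13%.

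A larger fall requires real recovery between the samples. If ALT is still rising, the substitution raises the mean.

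**The case against.** The case for leaving the rule alone is substantial.

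- **The liver signal is held elsewhere.** This stands. The worst-case grade summary uses unscheduled values, abnormal liver data are listed (SAP 4.3.2.2), clinically significant values are recorded as AEs (Protocol 8.3.4), and ALT of 3×ULN or more triggers a liver event form (Protocol 10.6). No hypothesis is tested, and no stated decision uses by-visit liver means. A reader might infer that abnormal liver results drop out of the safety evaluation; the documents do not support that.
- **The selection is not one-way.** This stands for monotherapy, where spill from Days 2 and 7 matches the direct effect. In follow-up the direct effect dominates.
- **Exposure in monotherapy is small.** Mostly stands. Chemistry is drawn at every visit, so a recheck after Day 3 or Day 8 may simply be the Day 6 or Day 11 visit. A next-day repeat needs a fast result and recall. The 33% belongs to follow-up, after cART has started, although Protocol 4.1 continues that follow-up so that study-drug concentrations can fall below quantification.
- **Local repeats are excluded from summaries (SAP 4.1.1).** True, but Protocol 10.6 directs liver follow-up to the central laboratory where possible, and Protocol 10.2 requires a central sample alongside any local one.
- **SAP 6.2.5 already takes the worst case.** In the legible text, only for samples on the same study day. The start of that section is redacted and the output specification is not public, so a further rule may exist there.

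A reader might also infer that Protocol 8.3.4 is at fault, or is the only source of repeats. It is an ordinary retest rule, and Sections 8 and 10.6 add others. The issue lies in SAP 6.2.4.

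**Conclusion.** The point holds in limited form. On the legible text, the value used for a by-visit liver summary can depend on whether the scheduled result was abnormal. Direct replacement needs three things together: a visit before the target day, a multi-day window, and a central-laboratory repeat nearer the target. The shares of about 33% (follow-up) and 11% (Days 4 and 9) are per triggering value with a repeat 1 to 3 days later. They rest wholly on the assumed uniform visit days and lags.

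The net tendency in follow-up is attenuation; for the Day 4 and Day 9 windows no net direction is shown. The repeat need not be normal, so displacement does not always remove the abnormality. The consequence is confined to one descriptive secondary display, but that display is a named endpoint and the remedy costs little.

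**What to change.** Add to SAP 6.2.4: by-visit laboratory summaries use the scheduled central-laboratory value; an unscheduled or repeat value is used only if the scheduled value in that window is missing or technically invalid; all other repeats contribute only to the worst-case grade summary and the listings.

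The exception for invalid samples is needed because Protocol Section 8 allows repeats for technical problems, and a compromised scheduled result should not outrank its valid repeat. The same edit should say whether the averaging rule in 6.2.4 or the worst-case rule in 6.2.5 governs same-day samples, since both can apply and no precedence is stated.

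The cost is a small programming change and occasional use of a value further from the target day. No new data are needed, repeats stay in the other displays, and the retest requirements in the protocol are untouched. The change should be made before database lock.
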